10.0 Efficacy Analysis

10.1 General Considerations

All efficacy analyses will be conducted on the intent-to-treat dataset unless otherwise specified. Data collected more than 45 days after the last dose of the study drug will not be included in efficacy analyses.

10.2 Primary Analysis of Primary Efficacy Endpoint

The primary efficacy endpoint is the change from baseline to Week 96 visit on the CDR--SB score. The primary analysis population will be subjects in the ITT dataset and the primary analysis will be a likelihood-based, mixed-effects model, repeated measures (MMRM) analysis of the change from baseline to each post-baseline assessment up to and including Week 96. The model will include fixed, categorical effects for treatment, site, visit, baseline score-by-visit and treatment-by-visit interactions, with continuous fixed covariate for baseline score. The primary comparison will be the contrast between each ABBV-8E12 dose group and placebo group at Week 96. Contrasts between each ABBV-8E12 dose group and placebo at Weeks 24, 48, 72, and overall across the treatment period will be obtained and will be considered as secondary. An unstructured (co)variance structure will be used to model the within-patient errors. The same (co)variance structure will also be used for all MMRM analyses for secondary efficacy variables. Satterthwaite's approximation will be used to estimate denominator degrees of freedom.

The following statistics will be presented on the statistical table of MMRM analysis for change from baseline to each visit (Weeks 24, 48, 72, and 96): descriptive statistics

(number of non-missing observations, mean, standard deviation, minimum and maximum) for each treatment group. Within group LS mean and standard error will be presented for each treatment group. LS mean, standard error, 95% confidence interval and two-sided *P* values for comparisons between each ABBV-8E12 dose group and placebo at each post-baseline visit will also be presented. The LS mean, standard error, 95% confidence interval and two-sided *P* values of treatment difference comparing each ABBV-8E12 dose group with placebo across the treatment period will be included in the output as well.

10.3 Secondary Efficacy Analysis

10.3.1 Analysis of Secondary Efficacy Variables

The secondary efficacy variables include:

- ADAS-Cog-14 total score and subscale scores
- FAQ total score
- ADCS-CGIC-MCI clinical global impression, cognition, behavior and functional abilities scores
- UPSA-Brief score
- ADCS-MCI-ADL-24 total score
- RBANS total scale score and subtest scores
- MMSE total score
- NPI total score
- ADCOMS

ADAS-Cog-14 total score and FAQ total score are key secondary efficacy variables and the Week 96 comparisons for each ABBV-8E12 dose vs placebo will be included in the multiplicity adjustment for the overall FWER control. Other secondary efficacy variables will not be included in the multiplicity adjustment for the overall FWER control. The MMRM method used for the primary efficacy analysis will be applied to analyze the change from the baseline to each post-baseline assessment up to and including Week 96 for these secondary variables with the exception of ADCS-CGIC-MCI scores for which

the dependent variable is ADCS-CGIC-MCI score itself. The model will include fixed, categorical effects for treatment, site, visit, baseline score-by-visit interaction and treatment-by-visit interactions, with continuous fixed covariate for baseline score in the model. For the MMRM analysis of ADCS-CGIC-MCI scores, there is no baseline score and no baseline score-by-visit interaction in the model. The comparison will be the contrast between each ABBV-8E12 dose group and placebo group at each post-baseline visit.

The following statistics will be presented in the statistical table of MMRM analysis for change from baseline to each post-baseline visit: descriptive statistics (number of non-missing observations, mean, standard deviation, minimum, and maximum) for each treatment group. Within group LS mean and standard error for each post-baseline visit will be presented for each treatment group. LS mean, standard error, 95% confidence interval and two-sided *P* values of treatment difference comparing each ABBV-8E12 dose group with placebo will also be presented for each post-baseline visit. The LS mean, standard error, 95% confidence interval and two-sided *P* values of treatment difference comparing each ABBV-8E12 dose group with placebo across the treatment period will be included in the output. *P*-values after considering multiplicity adjustment for the primary and key secondary variables will be presented in a separate table.

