Digital clock drawing	d	5	Patient	X	X	X	X	X	X	X	X

ADAS-Cog-14 = Alzheimer's Disease Assessment Scale (14-Item) Cognition portion; ADCS-CGIC-MCI = Alzheimer's Disease Cooperative Study Clinician's Global Impression of Change for Mild Cognitive Impairment; ADCS-MCI-ADL-24 = 24-item Alzheimer's Disease Cooperative Study/Activities of Daily Living Scale Adapted for Patients with Mild Cognitive Impairment; CDR = Clinical Dementia Rating; C-SSRS = Columbia-Suicide Severity Rating Scale; FAQ = Functional Activities Questionnaire; MHIS = Modified Hachinski Ischemic Scale; MMSE = Mini-Mental State Examination; N/A = not applicable; NPI = Neuropsychiatric Inventory; RBANS = Repeatable Battery for Assessment of Neuropsychological Status; UPSA Brief = University of California San Diego Performance Based Skills Assessment, Brief Version

- a. Breaks should be taken as necessary.
- b. Assessments will be done once during this time frame and can be administered on any day, but all must be done on the same day.
- c. The C-SSRS will be done at each visit throughout the study (see Study Activities Table [Appendix C](#) for all time points).
- d. Scale may be administered/assessed at any time during the visit.

I – Administered during Screening to assess inclusion criteria only.

The diagnostic tools and rating scales include the following:

Clinical Dementia Rating (CDR)¹²

The Clinical Dementia Rating (CDR) is a numeric scale used to quantify the severity of symptoms of dementia. A qualified health professional will assess a patient's cognitive and functional performance in six areas: memory, orientation, judgment and problem solving, community affairs, home and hobbies, and personal care. The CDR scale gives a score from 0 – 3 for each of the six areas. The sum of these six areas, the CDR sum of boxes (CDR-SB) score can range from 0 – 18.

Using a scoring algorithm, a CDR global score (range from 0 – 3) will be generated. The subject must have a CDR global score of 0.5 at Screening to be eligible for study participation. The CDR-SB score will be calculated at each time point. The CDR will be administered to both the patient and the study partner at the times indicated in [Table 4](#).

Alzheimer's Disease Assessment Scale (14-Item) Cognition Portion; (ADAS-Cog-14)¹³

The ADAS-Cog was designed to assess the cognitive impairments most common in AD. The ADAS-Cog is a subscale of the ADAS, which focuses on cognitive functioning and memory.

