The instrument covers four major domains: 1. General condition, 2. Cognition, 3. Behavior, and 4. Social and daily functioning. Scoring is based on a 7-point Likert Scale: 1, marked improvement; 2, moderate improvement; 3, minimal improvement; 4, no change; 5, minimal worsening; 6, moderate worsening; 7, marked worsening. Higher score indicates greater worsening.

At baseline, the clinician interviews the subject and study partner about baseline status for later reference. At baseline only, clinical information about the subject may be used, including medical history, physical and neurological examination, and other ratings done at screening. At interval assessments, the subject is interviewed first, followed by the informant. After completing the worksheets, the clinician records his/her clinical impression of change from baseline on the 7-item scale, referring only to his/her own baseline information when making the assessment, without consulting other study personnel and blinded to possible medication or adverse effects. The instrument has 5-items for baseline and 4-items for the post-baseline assessment. The ADCS-CGIC-MCI will be administered to both the patient and the study partner at the times indicated in [Table 4](#).

Modified Hachinski Ischemic Scale (MHIS)^{26,27}

The MHIS is a brief clinical scale used to distinguish vascular dementia from non-vascular dementia by assessing the presence of concurrent vascular risk factors, focal neurological symptoms or signs suggestive of prior stroke, or a history of strokes. An experienced clinician will assess the MHIS for all subjects. Subjects must have a score ≤ 4 to be eligible for study participation. The MHIS will be administered at the times indicated in [Table 4](#).

Repeatable Battery for Assessment of Neuropsychological Status (RBANS)²⁸

The Repeatable Battery for the Assessment of Neuropsychological Status (RBANS) is a 25-minute, standardized neurocognitive battery with North American population-based normative data. The RBANS measures five neurocognitive domains, with age-based scaling. Twelve subtests measure cognitive decline or improvement across the following domains:

1. Immediate Memory – List Learning and Story Memory,
2. Visuospatial/Constructional – Figure Copy and Line Orientation,
3. Language – Picture naming and Semantic Fluency,

4. Attention – Digit Span and Coding, and
5. Delayed Memory – List Recall, List Recognition, Story Memory, and Figure Recall.

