8.1.3.2 Secondary Efficacy Analysis

Secondary Efficacy Analysis of the Primary Efficacy Variable

The change from baseline to each post-baseline observation on the CDR-SB scores will be summarized. The change from baseline to final observation up to Week 96 on the CDR-SB score will be analyzed by an analysis of covariance (ANCOVA) model with treatment and study site as the main effects and the baseline CDR-SB score as covariate.

Analyses for Secondary Efficacy Variables

The other secondary efficacy variables include ADAS-Cog-14 total score, scores of MMSE, NPI and ADCS-MCI-ADL-24 and scores of FAQ, UPSA-Brief, RBANS and ADCS-CGIC-MCI.

The change from baseline score on each secondary efficacy variable (with the exception of ADCS-CGIC-MCI) will be summarized and analyzed using the similar MMRM model described for the primary efficacy analysis. The change from baseline to final observation

up to Week 96 for each secondary efficacy variable (with the exception of ADCS-CGIC-MCI) will also be analyzed using an ANCOVA model with treatment and study site as the main effects and the baseline value of analyzed variable as a covariate.

The ADCS-CGIC-MCI score at each visit up to Week 96 will be summarized and analyzed using an MMRM model with fixed, categorical effects for treatment, site, visit and treatment-by-visit interaction. The final ADCS-CGIC-MCI score up to Week 96 will be analyzed using an ANCOVA model with treatment and study site as the main effects.

The analyses will be performed in the ITT data set.

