7.1 Demographic and Baseline Characteristics

The following demographic and baseline characteristics will be summarized for each treatment group, for the combination of all ABBV-8E12 dose groups ("ABBV-8E12 Overall") and for the combination of all treatment groups ("Total Subjects") for the safety dataset.

- Gender (male/female)
- Race (white, black, American Indian/Alaska native, Native Hawaiian or other Pacific Islander, Asian, Other, Multi-Race)
- Education (high school or above, lower than high school)
- Ethnicity (Hispanic or Latino)
- Age (years)
- Age group (< 65, ≥ 65)
- Weight for all subjects (kg)
- Weight for all male subjects (kg)
- Weight for all female subjects (kg)
- Height (cm)
- Body mass index (BMI, kg/m²)
- Body mass index category (BMI, kg/m²) (< 25, ≥ 25)
- APOE allele status (ε2ε2, ε2ε3, ε2ε4, ε3ε3, ε3ε4, ε4ε4)

- Baseline AD medication use: AChEI (donepezil, rivastigmine, galantamine) and memantine

Alcohol and tobacco uses will be summarized for each treatment group, ABBV-8E12 Overall and Total Subjects for the safety dataset. For alcohol use, the number and percentage of subjects who are drinkers, ex-drinkers and non-drinkers (defined as those who have never been a drinker) will be presented. For the tobacco use, the number and percentage of users, ex-users and non-users (defined as those who have never been a user) will be presented. A subject reporting multiple use categories for the different types of tobacco (cigarette, pipe, cigar and chewing tobacco) will be counted in the tobacco user category.

The following baseline efficacy variables will be summarized for each treatment group, ABBV-8E12 Overall and Total Subjects for the ITT dataset.

- CDR-SB score
- ADAS-Cog-14 total score and subscale scores
- FAQ total score
- UPSA-Brief score
- ADCS-MCI-ADL-24 total score
- RBANS total scale score and subtest scores
- MMSE total score
- NPI total score
- ADCOMS score

ADCOMS score is a composite score which is a weighted linear combination of the remaining individual scale items from ADAS-cog, MMSE, and CDR-SB scales. The weights for items are listed below.³

Scale	Item name	Weights
ADAS-cog	Delayed word recall	0.008
	Orientation	0.017
	Word recognition	0.004
	Word finding difficulty	0.016
MMSE	Orientation time	0.042
	Drawing	0.038
CDR-SB	Personal care	0.054
	Community affairs	0.109
	Home and hobbies	0.089
	Judgement and problem solving	0.069
	Memory	0.059
	Orientation	0.078

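### The ADCS-CGIC-MCI model carries no baseline severity covariate; prespecifying baseline CDR-SB costs almost nothing and may gain some precision

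*SAP*

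**What the plan says.** The ADCS-CGIC-MCI is a 7-point rating in which, per Protocol 5.3.1.1, "the clinician records his/her clinical impression of change from baseline on the 7-item scale". It is rated after baseline at Weeks 48 and 96 only (Protocol Table 4, SAP Table 3).

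- **SAP 10.3.1:** for the repeated-measures analysis of this scale, "there is no baseline score and no baseline score-by-visit interaction in the model".
- **Protocol 8.1.3.2:** the score at each visit is "analyzed using an MMRM model with fixed, categorical effects for treatment, site, visit and treatment-by-visit interaction". The protocol adds a second analysis: "The final ADCS-CGIC-MCI score up to Week 96 will be analyzed using an ANCOVA model with treatment and study site as the main effects".

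No other baseline severity variable is named for this scale. By contrast, the primary model (SAP 10.2) and the model for the other secondary variables (SAP 10.3.1) each include the corresponding baseline score and its interaction with visit.

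CDR is scheduled for all subjects at Screening and again between Day -7 and Day 1. Protocol 5.3.1.1 adds: "The CDR-SB score will be calculated at each time point". SAP 7.1 opens its list of baseline scores with CDR-SB, under this sentence: "The following baseline efficacy variables will be summarized for each treatment group, ABBV-8E12 Overall and Total Subjects for the ITT dataset". SAP 6.2 defines baseline as the last non-missing value before the first dose.

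The objectives (Protocol 4.0, SAP 4.1) name ADCS-CGIC-MCI as the sole measure of global impact. SAP 10.3.1 keeps it outside the multiplicity adjustment, which covers ADAS-Cog-14 and FAQ as the key secondary variables.

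**The concern.** The scale's lack of a baseline value explains why its own baseline is not in the model. It does not explain why no severity covariate is used at all. The plan already substitutes a covariate where an outcome's own baseline is not used: for the CSF ratio of free to total tau, the covariate is baseline total tau (Protocol 8.1.5, SAP 13.0).

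Two things are at stake, both modest. First, any variance in the score that baseline severity would explain stays in the error term. Second, randomization is stratified by site only (Protocol 8.3, SAP 5.1), so a chance difference in severity between arms would pass into the estimate uncorrected. In addition, if baseline severity also predicts dropout, including it would make the missing-at-random assumption more plausible. That matters more for a scale with two post-baseline visits than for one with four.

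**Working it through.** **The plan's own figure.** The documents give no standard deviation, power or precision for ADCS-CGIC-MCI. The only sample-size figure is for CDR-SB (Protocol 8.2, SAP 4.3): 100 per group, 25% without post-baseline data, effect sizes 0.45, 0.45 and 0.28, one-sided 2.5% with Bonferroni, and about 80% power.

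- Evaluable per arm: 100 × (1 − 0.25) = 75.
- With 75 per arm and 0.025/3 per dose, power is 64.1% for each of the two higher doses and 24.8% for the low dose.
- Simulating three comparisons that share one placebo arm, power to reject for at least one dose is 80.6%. With 100 per arm it would be 90.8%.

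So the stated 80% reproduces as power for at least one dose, and 75 per arm is the number behind it. I use 75 below, assuming that it carries over to ADCS-CGIC-MCI.

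**Effect of adding baseline CDR-SB.** Let r be the partial correlation between baseline CDR-SB and the Week 96 score, given site. Site is already in the model, so the partial correlation is the relevant one.

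- Residual variance ratio = 1 − r²
- SE ratio = √(1 − r²)
- Equivalent evaluable n per arm = 75 / (1 − r²)

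The documents do not give r. It is an assumption, shown from zero upward.

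| Assumed r | 1 − r² | SE ratio | SE reduction | Equivalent n per arm |
|---|---|---|---|---|
| 0 | 1.00 | 1.0000 | 0% | 75.0 |
| 0.1 | 0.99 | 0.9950 | 0.50% | 75.8 |
| 0.2 | 0.96 | 0.9798 | 2.02% | 78.1 |
| 0.3 | 0.91 | 0.9539 | 4.61% | 82.4 |
| 0.4 | 0.84 | 0.9165 | 8.35% | 89.3 |

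The formula treats the Week 96 contrast as a single-visit comparison and ignores the few degrees of freedom spent. Both are acceptable simplifications for a question of this size.

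**Where r may lie.** Entry narrows the range of severity: "The subject must have a CDR global score of 0.5 at Screening to be eligible for study participation", and MMSE must be 22 to 30 (Protocol 5.2.1). A narrow baseline range tends to weaken a correlation. The outcome is also a rating of change made against the clinician's own baseline notes, so a link to starting severity cannot be presumed. Values near zero therefore belong in the table.

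**Cost in parameters.** With two post-baseline visits, baseline CDR-SB and its interaction with visit amount to two slopes.

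**The case against.** The strongest reply is that nothing here is an error. The scale has no baseline score, both documents specify the same repeated-measures model, and the SAP states the omission openly. All of that stands.

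A reader might infer that the unadjusted treatment comparison is biased. The documents do not support that: subjects are randomized, so the contrast is valid without the covariate.

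A reader might also infer that the intervals are wider by a known amount. They are not. The loss depends on r, which is not given and could be near zero.

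A third tempting statement is that baseline CDR-SB is available for every ITT subject. The documents show only that it is scheduled for all. SAP 10.4.2 allows for subjects with no baseline observation. Such cases should be rare because a screening CDR is required for entry, but adding the covariate would drop them from a model that now keeps them.

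Three further points limit the importance:

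- The endpoint is outside familywise error control, so no confirmatory conclusion can change.
- Baseline CDR-SB is tabulated by arm, so a material imbalance would be visible, though the estimate would not be adjusted for it.
- Baseline ADAS-Cog-14, MMSE, FAQ or ADCS-MCI-ADL-24 could serve instead. CDR-SB is a reasonable choice because it is the primary scale and covers both cognition and function, but it is not the only defensible one.

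None of these points shows that adding a prespecified, already collected covariate would do harm.

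**Conclusion.** The point holds as a minor, low-cost improvement. Neither document gives the ADCS-CGIC-MCI model a baseline severity covariate, although one is scheduled for all subjects and the plan uses a substitute covariate elsewhere. The benefit is an SE reduction of 0% to 8.35% for an assumed partial correlation of 0 to 0.4, and about 2% or less if the correlation is 0.2 or below. In sample-size terms that is the equivalent of 0 to about 14 extra evaluable subjects per arm (89.3 − 75 = 14.3). This rests on 75 evaluable per arm and on a correlation that the documents do not supply. Validity, type I error control and the primary and key secondary conclusions are unaffected.

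**What to change.** Before unblinding, amend SAP 10.3.1 so that the ADCS-CGIC-MCI model includes baseline CDR-SB (the last non-missing pre-dose value) and baseline CDR-SB-by-visit as fixed covariates, and apply this to all four ADCS-CGIC-MCI scores. Record the departure from Protocol 8.1.3.2 in SAP 14.0. The covariate has to be fixed in advance, since one chosen after unblinding would not be credible.

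The cost is one SAP sentence, two slopes per model, and the loss of any rare subject with no pre-dose CDR-SB. No new data are needed. If r is close to zero, almost nothing is lost.

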10.4 Additional Efficacy Analysis

10.4.1 Sensitivity analysis of CDR-SB score

Sensitivity analyses of CDR-SB score change from baseline will be conducted in ITT dataset in the final analysis. Subjects who are randomized and dosed but failed to meet all inclusion criteria or met any exclusion criteria will be excluded from these analyses. In addition, the impact of COVID-19 on data collection in Study M15-566 should be considered as well. The following sensitivity analyses on CDR-SB score may be conducted:

- Sensitivity analysis I: excluding subjects from ABBV-8E12 groups who missed more than two doses than expected (subjects who complete Week 96

visit and receive less than 22 doses, subjects who are prematurely discontinued and receive more than two doses less than expected before the discontinue visit date) or received less than 80% amount dosage than the assigned amount for more than two doses during the double-blind period.

- Sensitivity analysis II: include all subjects who have available CDR-SB score change from baseline regardless how many doses are missed or under-dosed or records are more than 45 days after the last dosing.

The MMRM analysis will be applied for these analyses and similar output will be generated for the sensitivity analyses of CDR-SB score. No multiplicity adjustment is needed for these analyses.

Sensitivity analysis will also be conducted on the CDR-SB score to evaluate the impact of missing data on the primary efficacy results. Details of sensitivity analysis for missing data are specified in Section 10.6 of the SAP.

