5.5 Treatments

5.5.1 Treatments Administered

ABBV-8E12 will be given by IV infusion. Subject weight will be obtained prior to study drug administration to determine the appropriate infusion rate as shown in the table below.

Subject's Weight in kg	Infusion Rate*
26.0 – 34.9 kg (inclusive)	2.1 mL/min or 126 mL/hr
35.0 – 44.9 kg (inclusive)	2.8 mL/min or 168 mL/hr
45.0 – 59.9 kg (inclusive)	3.6 mL/min or 216 mL/hr
60.0 – 89.9 kg (inclusive)	4.8 mL/min or 288 mL/hr
90.0 kg and over	7.2 mL/min or 432 mL/hr

* Continue infusion until bag is empty.

Study drug will be administered by IV infusion, preferably in the morning but should be around the same time at each visit as follows:

Study Drug	Formulation
Placebo (0.9% Sodium Chloride Injection/Solution for Infusion)	IV infusion every 4 weeks for 96 weeks (Total of 24 infusions)
ABBV-8E12 300 mg	
ABBV-8E12 1000 mg	
ABBV-8E12 2000 mg	

Doses may be modified after evaluation by the data monitoring committee of the safety, tolerability and available pharmacokinetic data.

The start and stop time of each study drug infusion will be recorded to the nearest minute. The start of study drug infusion occurs from ABBV-8E12 initiation up until the administration of the complete dose (including flush). The Pharmacy Manual may be referred to for detailed instructions.

Home Healthcare Service Due to the COVID-19 Pandemic

Subjects may be offered the option of home healthcare visits provided by a study nurse or third-party vendor based on the subject's suitability as assessed by the investigator and following the subject's written consent. This option can only be offered in countries and sites that comply with local regulatory and IEC/IRB requirements for home healthcare. Any prerequisite submissions or notifications to the site IEC/IRB and local competent health authority should be made and approved prior to the implementation of home infusions.

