5.5.5 Blinding

Placebo solution will be essentially identical in volume to the ABBV-8E12 solution. The Investigator, study site personnel (except the unblinded pharmacist) and the subject will remain blinded to the treatment throughout the course of the study. The study sponsor will remain blinded; however, a pharmacokineticist will be provided individual pharmacokinetic data from Cohort 1 after 48 weeks of treatment. Subject identification numbers will be changed for the pharmacokinetic analysis to maintain the sponsor blind.

ABBV-8E12 and 0.9% Sodium Chloride Injection/Solution for Infusion (if applicable) will be delivered to the unblinded pharmacist or qualified designee in an open-label format. The unblinded pharmacist or qualified designee will prepare the dosing of ABBV-8E12 (in a blinded manner) following the available preparation instructions as appropriate based on the subject's assigned treatment group. For blinding purposes, identical commercial 0.9% Sodium Chloride Injection/Solution for Infusion bag or bottle will be used in the placebo and ABBV-8E12 arms at each site. The unblinded pharmacist or qualified designee will place a blinding bag over the infusion bag or bottle before dispensation following the written instructions provided as a separate document from the protocol.

For investigational product monitoring, there will be an unblinded clinical research associate (CRA) for verification of unblinded documentation. The unblinding procedure for the unblinded pharmacist/designee and the unblinded CRA will be defined in a separate study-specific document.

The IVR system will be programmed with blind-breaker instructions. The study blind for a subject may be broken, if, in the opinion of the investigator, it is in the subject's best interest to know the study drug assignment.

AbbVie must be notified before breaking the blind, unless identification of the study drug is required for a medical emergency, i.e., situation in which the knowledge or the specific blinded treatment will affect the immediate management of the subject's conditions (e.g., antidote is available). AbbVie must then be notified within 24 hours of the blind being broken. The date and reason that the blind was broken must be recorded in the source documentation and on the eCRF, as applicable.

Unblinding of Data for the Data Monitoring Committee (DMC)

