8.1.6 Safety Analyses

All safety analysis will be performed on the safety data set unless otherwise specified. Comparisons between each ABBV-8E12 dose group and placebo will be performed with two-sided test at the significance level of 0.05, if applicable. Pairwise comparisons for each ABBV-8E12 dose group versus placebo will be evaluated.

All safety assessments that are taken no more than 20 weeks after the last dose of study drug will be included in the safety evaluation for subjects who complete the double-blind Treatment Period or PD and do not roll over to the planned extension study. If subjects enroll in the planned extension study, their safety information collected before the first dose of the planned extension study will be included in the safety evaluation for the double-blinded period.

Study Drug Exposure and Compliance

The number of doses on study drug will be summarized by treatment group and all treatment groups combined. The number and percentage of subjects with at least 90% compliance with study drug (i.e., complete 90% of scheduled doses) will be summarized by treatment group and all treatment groups combined.

Adverse Events

A treatment-emergent adverse event (TEAE) is defined as any adverse event that begins or worsens in severity on or after the first study drug dose date and no more than 20 weeks after the last study drug dose date.

Unless otherwise specified, the treatment group differences in continuous safety variables (e.g., change from baseline to final observation on laboratory tests) will be assessed using an ANOVA model with the term of treatment, and the treatment group differences in binary safety variables will be evaluated using a Fisher's exact test.

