9.0 Study Drug Exposure and Compliance

Summaries of study drug exposure and compliance will be prepared for the safety dataset.

Study drug exposure will be summarized for each ABBV-8E12 treatment group, ABBV-8E12 Overall. Duration of exposure is calculated as the last study drug administration date minus the first study drug administration date + 30. Total subject years of exposure is calculated by summing the duration of exposure across all subjects and dividing this sum by 365 (1 year will be considered to be 365 days). The number and percentage of subjects who have taken a total of 1, 2, 3, 4 - 6, 7 - 9, 10 - 12, 13 - 15, 16 - 18, 19 - 21, 22 - 24, > 24 infusions of study drug will be summarized. No comparisons of treatment groups will be performed for this summary. In addition, duration of exposure will be summarized with descriptive statistics (number of non-missing observations, mean, standard deviation, median, minimum and maximum duration, and total subject-years).

To evaluate impact of COVID-19 pandemic on study drug compliance, expected infusions (completers are expected to have 24 infusions, prematurely discontinued subjects are expected to have expected number of infusions based on discontinuation visit date) and infusions missed due to COVID-19 pandemic will be summarized for each ABBV-8E12 treatment group and ABBV-8E12 Overall (mean, minimum, maximum of expected infusions; mean, minimum, maximum of missed infusions, mean of the percentage of missed infusions relative to expected number of infusions will be tabulated) across all countries and by country.

At each scheduled dosing visit for ABBV-8E12 groups, the investigator will document whether the subject has received the entire dose infusion or not and the volume administered will be recorded in the eCRF if the entire dose is not administered. The percentage of the assigned dose administered will be calculated at each visit. The mean of

this percentage across infusions for each subject will be obtained. The descriptive statistics (number of non-missing observations, minimum, mean, median, standard deviation, maximum) based on each subject's mean volume percentage of study drug infusion will be summarized for each ABBV-8E12 treatment group and ABBV-8E12 Overall.

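### Sensitivity analysis I removes under-dosed subjects from the ABBV-8E12 arms but keeps their placebo counterparts

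*SAP*

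**What the plan says.** SAP 10.4.1 lists two sensitivity analyses of CDR-SB that may be conducted, both with the MMRM.

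- Analysis I works by "excluding subjects from ABBV-8E12 groups who missed more than two doses than expected". For a subject who completes Week 96, this means one who reaches that "visit and receive less than 22 doses". Subjects who stop early are judged only against the doses expected before their discontinuation visit. A second criterion removes subjects given less than 80% of the assigned amount at more than two infusions.
- Analysis II applies no dosing exclusion in any arm.
- Eligibility violators are excluded from both analyses, whatever their arm.
- On error control the section says: "No multiplicity adjustment is needed for these analyses".

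SAP 9.0 has the same one-sided wording. On completeness of infusion: "At each scheduled dosing visit for ABBV-8E12 groups, the investigator will document whether the subject has received the entire dose infusion". On missed infusions: "infusions missed due to COVID-19 pandemic will be summarized for each ABBV-8E12 treatment group and ABBV-8E12 Overall".

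The protocol treats the arms alike. The treatment table in 5.5.1 gives placebo and the three doses the same 24 infusions, and 5.5.5 states: "Placebo solution will be essentially identical in volume to the ABBV-8E12 solution". Protocol 8.1.6 plans exposure and compliance for every arm: "The number of doses on study drug will be summarized by treatment group and all treatment groups combined".

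**The concern.** Placebo subjects can miss or cut short infusions just as drug subjects can, so the rule could be applied to every arm. As written, only the drug arms lose their poor compliers.

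Compliance arises after randomisation, and poor compliers may differ in prognosis. Protocol 5.4.1 gives one possible link: subjects with unexpected cognitive worsening continue only after a management plan is discussed. The MMRM in SAP 10.2 adjusts for baseline score and site, but not for dosing history.

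If the analysis is run, its LS mean differences, 95% confidence intervals and two-sided P values would stand beside the primary result. A shift produced by the exclusion alone could then be read as a benefit of adequate dosing. With placebo absent from the SAP 9.0 summaries, a reader could not tell whether under-dosing was balanced across arms.

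**Working it through.** **Inputs from the plan.** SAP 4.3 gives 100 subjects per arm, 25% without post-baseline data, planning effects of 0.45 (high and middle dose) and 0.28 (low dose), and a one-sided 2.5% level with Bonferroni adjustment. Hence n = 100 × (1 − 0.25) = 75 per arm.

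**The plan's own figure.** With 75 per arm, a shared placebo group, those effects and a level of 0.025/3 per dose, the simulated probability that at least one dose is significant is 80.6%. This agrees with the stated power of about 80%, so 75 per arm is a fair basis for what follows.

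**Assumed inputs.** The documents do not give p, the share of each arm meeting the exclusion, or g, the extra CDR-SB worsening of excluded over retained subjects in SD units. Both are assumptions, so a range is shown.

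**Bias with no drug effect.** Let the retained subjects have mean m.

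- Drug arm after exclusion: m.
- Placebo arm, nobody excluded: (1 − p)m + p(m + g) = m + pg.
- Drug minus placebo: −pg. A negative value favours ABBV-8E12.

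**Standard error and error rate.**

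- SE (drug arms only) = √(1/75 + 1/(75(1 − p)))
- Two-sided error = 1 − Φ(1.96 − pg/SE) + Φ(−1.96 − pg/SE)

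For p = 0.20 and g = 0.50:

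- SE = √(1/75 + 1/60) = 0.173, and pg/SE = 0.10/0.173 = 0.577.
- Error = 0.0834 (favouring drug) + 0.0056 = 0.0890.
- Against the planning effects: 0.10/0.45 = 22% and 0.10/0.28 = 36%.

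| p | g (SD) | Bias (SD) | Two-sided error |
|---|---|---|---|
| any | 0 | 0 | 5.0% |
| 5% | 0.25 | −0.0125 | 5.1% |
| 10% | 0.25 | −0.025 | 5.3% |
| 20% | 0.50 | −0.10 | 8.9% |
| 30% | 0.75 | −0.225 | 24% |

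The formula is symmetric. A negative g of the same size gives the same error rate, with the bias against ABBV-8E12.

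**Check with baseline adjustment.** The formula is for an unadjusted contrast. A simulation with a baseline-adjusted ANCOVA standing in for the Week 96 MMRM contrast (75 per arm, 20,000 runs) gave:

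- p = 10%, g = 0.5: error 6.1%
- p = 20%, g = 0.5: bias −0.10 SD, error 8.5%
- p = 30%, g = 0.5: error 12.7%
- p = 20%, g = 1.0: bias −0.20 SD, error 19.4%
- under-dosing dependent on baseline score only: bias about 0.001 SD, error 5.0%

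**Same rule in every arm.** In the same simulation the mean contrast lay between −0.001 and +0.002 SD and the error between 4.7% and 5.2%. This holds when under-dosing arises in the same way in all arms.

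**The case against.** The strongest reply is that little depends on this analysis. It is optional, carries no alpha and feeds neither the hypotheses nor the boundaries in SAP 10.7. Analysis II and the ITT primary analysis provide comparison points. That is correct and limits the severity, but neither comparison corrects the one-sided rule.

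A second reply is that the gap g may be close to zero. Many missed infusions may be logistical consequences of COVID-19, and SAP 10.6 argues that pandemic-related missing data are missing at random. The link through unexpected worsening is also weak, because it leads mainly to stopping treatment, and the rule does not count doses after the discontinuation visit. Both points are fair reasons not to assume a large bias. However, SAP 10.6 concerns missed visits and missing data, not the removal of treated subjects from some arms, and the exclusion counts every missed dose whatever its cause.

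A third reply is that the bias requires a relation between under-dosing and decline beyond baseline score and site. This stands, and the conclusion is worded accordingly.

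It could also be said that missing placebo infusions are pharmacologically irrelevant. That is true of exposure, but the rule also selects people, and comparable people require the same rule in placebo.

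Finally, the SAP 9.0 wording is a descriptive matter that biases no contrast by itself. It belongs here because the symmetric rule needs placebo infusion data to be summarised.

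**Conclusion.** The concern holds. As written, analysis I compares a compliance-selected drug group with an unselected placebo group, and no text in either document corrects this. The bias is pg: zero if under-dosing is unrelated to decline given baseline score and site, in the drug's favour if under-dosed subjects decline faster, and against it if they decline more slowly. At the illustrative 20% and 0.5 SD it is 0.10 SD, with a two-sided error of 8.9% by formula and 8.5% with baseline adjustment. Small inputs do little harm. These sizes rest on assumed p and g, 75 evaluable subjects per arm and no drug effect. The asymmetry itself rests only on the SAP text. It should be fixed, but it does not touch the primary ITT analysis, the key secondary tests or the interim boundaries.

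**What to change.** 1. In SAP 10.4.1, state that the missed-infusion and under-80% criteria of analysis I apply to all treatment groups including placebo, using placebo infusion counts and volumes.
2. In SAP 9.0, extend the exposure, missed-infusion and infusion-volume text to every treatment group including placebo, in line with Protocol 8.1.6.
3. State in SAP 10.4.1 that analysis I is supportive because it conditions on post-randomisation compliance, and that the number excluded and the reasons will be tabulated by arm. Symmetric exclusion does not remove bias if the drug itself affects compliance; the table would show whether that is a worry.

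The cost is a few wording edits. No extra data collection is expected, since blinded investigators could hardly record completeness for the drug arms alone. This is an inference from the blinding, because the eCRF is not among the documents.

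The placebo arm loses about p × 75 subjects from this one analysis: about 4 at 5%, 15 at 20%, and 22 to 23 at 30%. The standard error becomes √(2/(75(1 − p))), a rise of 1.3%, 5.4% and 8.5% respectively; at 20% it goes from 0.173 to 0.183 SD.
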